9.3. Categorical Classes for ECG and Vital Signs

Categories for QTcB and QTcF

QTcB/QTcF (ms)	max. \leq 450	450 $<$ max. \leq 480	480 $<$ max. \leq 500	max. $>$ 500
QTcB/QTcF (ms) increase from baseline	max. $<$ 30	30 \leq max. $<$ 60	max. \geq 60	

Categories for PR and QRS

PR (ms)	max \geq 300	
PR (ms) increase from baseline	Baseline $>$ 200 and max. \geq 25% increase	Baseline \leq 200 and max. \geq 50% increase
QRS (ms)	max \geq 200	
QRS (ms) increase from baseline	Baseline $>$ 100 and max. \geq 25% increase	Baseline \leq 100 and max. \geq 50% increase

Categories for Vital Signs

Systolic BP (mm Hg)	min. <90	
Systolic BP (mm Hg) change from baseline	max. decrease ≥30	max. increase ≥30
Diastolic BP (mm Hg)	min. <50	
Diastolic BP (mm Hg) change from baseline	max. decrease ≥20	max. increase ≥20
Supine pulse rate (bpm)	min. <40	max. >120

9.4. RECIST 1.1 Tumor Assessment Criteria

At baseline, individual tumor lesions will be categorized by the investigator as either measurable or not, according to the criteria summarized below:

Measurable Lesions

Lesions that can be accurately measured in at least one dimension (longest diameter in the plane of measurement is to be recorded) with a minimum size of:

- 10 mm for lesions other than lymph nodes and assessed by CT scan (CT scan slice thickness no greater than 5 mm).
- 10 mm for lesions assessed clinically by caliper measurement (lesions which cannot be accurately measured with calipers should be recorded as non-measurable).
- 20 mm for lesions assessed by chest X-ray.
- 15 mm in short axis for lymph nodes when assessed by CT scan (CT scan slice thickness recommended to be no greater than 5 mm).

Non-measurable Lesions

Non-measurable lesions include small lesions (longest diameter <10 mm or pathological lymph nodes with a ≥10 but <15 mm short axis) as well as truly non-measurable lesions. Truly non-measurable lesions include: leptomeningeal disease, ascites, pleural or pericardial effusion, inflammatory breast disease, lymphangitic involvement of skin or lung, abdominal masses identified by physical exam and not measurable by reproducible imaging techniques.

Nodes that have a short axis <10 mm are considered non-pathological and should not be recorded or followed.

Special Considerations Regarding Specific Lesions

Bone lesions:

- Bone scan, PET scan or plain films are not considered adequate imaging techniques to measure bone lesions. However, these techniques can be used to confirm the presence or disappearance of bone lesions.
- Lytic bone lesions or mixed lytic-blastic lesions, with identifiable soft tissue components, that can be evaluated by cross sectional imaging techniques such as CT or MRI can be considered as measurable lesions if the soft tissue component meets the definition of measurability described above.
- Blastic bone lesions are non-measurable.

Cystic lesions:

- Lesions that meet the criteria for radiographically defined simple cysts should not be considered as malignant lesions (neither measurable nor non-measurable) since they are, by definition, simple cysts.
- ‘Cystic lesions’ thought to represent cystic metastases can be considered as measurable lesions, if they meet the definition of measurability described above. However, if non-cystic lesions are present in the same patient, these are preferred for selection as target lesions.

Lesions with prior local treatment:

- Tumor lesions situated in a previously irradiated area, or in an area subjected to other loco-regional therapy, are usually not considered measurable unless there has been demonstrated progression in the lesion.

Solitary lesions:

If a measurable disease is restricted to a solitary lesion, its neoplastic nature should be confirmed by cytology/histology.

Recording Tumor Measurements

All measurable lesions up to a maximum of 2 lesions per organ and up to 5 in total and representative of all involved organs should be identified as **target lesions** and measured and recorded at baseline and at the stipulated intervals during treatment. Target lesions should be selected on the basis of their size (lesions with the longest diameters) and their suitability for accurate repetitive measurements (either by imaging techniques or clinically).

The longest diameter will be recorded for each target lesion. The sum of the longest diameter of all target lesions will be calculated and recorded as the baseline sum diameter to be used as reference to further characterize the objective tumor response of the measurable dimension of the disease during treatment.

One exception to the above described approach is related to pathological lymph nodes. Pathological lymph nodes are defined as measurable lesions and may be identified as target lesions if the criterion of a short axis of ≥ 15 mm by CT scan is met. Only the short axis of these nodes will contribute to the baseline sum. Nodal size is normally reported as two dimensions in the plane in which the image is obtained (for CT scan this is almost always the axial plane; for MRI the plane of acquisition may be axial, sagittal or coronal). The smaller of these measures is the short axis.

A sum of the diameters (longest for non-nodal lesions, short axis for nodal lesions) for all target lesions will be calculated and reported as the baseline sum diameters. The baseline sum diameters will be used as reference to further characterize any objective tumor regression in the measurable dimension of the disease.

All other lesions (or sites of disease) should be identified as **non-target lesions** and should also be recorded at baseline. Measurements are not required and these lesions should be followed as ‘present’, ‘absent’, or in rare cases ‘unequivocal progression’. In addition, it is possible to record multiple non-target lesions involving the same organ as a single item on the case record form (eg, ‘multiple enlarged pelvic lymph nodes’ or ‘multiple liver metastases’).

Definition of Tumor Response

Target Lesions

Response in target lesions is defined as follows:

- **Complete Response (CR):** disappearance of all target lesions.
- **Partial Response (PR):** at least a 30% decrease in the sum of diameters of target lesions, taking as reference the baseline sum diameters.
- **Progressive Disease (PD):** at least a 20% increase in the sum of diameters of target lesions, taking as reference the smallest sum on study (this includes the baseline sum if that is the smallest on study). In addition to the relative increase of 20%, the sum must also demonstrate an absolute increase of at least 5 mm. The appearance of one or more new lesions is also considered a sign of progression.
- **Stable Disease (SD):** neither sufficient shrinkage to qualify for PR nor sufficient increase to qualify for PD, taking as reference the smallest sum diameters while on study.

When nodal disease is included in the sum of target lesions and the nodes decrease to 'normal' size (<10 mm), they may still have a measurement reported on scans. This measurement should be recorded even though the nodes are normal in order not to overstate progression should it be based on increase in size of the nodes. As noted earlier, this means that patients with CR may not have a total sum of 'zero' on the CRF.

Non-Target Lesions

While some non-target lesions may actually be measurable, they need not be measured and instead should be assessed only qualitatively at the time points specified in the protocol.

Response in non-target lesions is defined as follows:

- **Complete Response (CR):** Disappearance of all non-target lesions and normalization of tumor marker level. All lymph nodes must be non-pathological in size (<10 mm short axis).
- **Non-CR/Non-PD:** Persistence of one or more non-target lesion(s) and/or maintenance of tumor marker level above the normal limits.
- **Progressive Disease (PD):** Unequivocal progression of existing non-target lesions. (Note: the appearance of one or more new lesions is also considered progression).

Cytology, histology

These techniques can be used to differentiate between PR and CR in rare cases if required by protocol (for example, residual lesions in germ cell tumors). When effusions are known to be a potential adverse effect of treatment (eg, taxane compounds or angiogenesis inhibitors), the cytological confirmation of the neoplastic origin of any effusion that appears or worsens during treatment can be considered if the measurable tumor has met criteria for response or stable disease in order to differentiate between response or stable disease and progressive disease.

For patients having effusions or ascites, only cases having cytological proof of malignancy should be recorded on the CRF. Effusions that have not been evaluated using cytology or were found to be non-malignant should not be recorded on the CRF.

New Lesions

The appearance of new malignant lesions indicates PD. New lesion should be unequivocal (eg, not attributable to differences in imaging technique, or change in imaging modality or findings not attributable to tumor). If a new lesion is equivocal, for example due to its small size, continued therapy and follow-up assessment will clarify the etiology of the disease. If repeat scans confirm there is definitely a new lesion, then progression should be declared using the date of the initial scan.

The use of FDG-PET is sometimes reasonable to complement a CT scan assessment of a PD (particularly for possible ‘new’ disease). New lesions on the basis of FDG-PET imaging can be identified according to the following algorithm:

- Negative FDG-PET at baseline, with a positive FDG-PET at follow-up.
- No FDG-PET at baseline and a positive FDG-PET at follow-up: if the positive FDG-PET at follow-up corresponds to a new site of disease confirmed by CT, this is PD.

If the positive FDG-PET at follow-up is not confirmed as a new site of disease on CT, additional follow-up CT scans are needed to determine if there is truly progression occurring at that site (if so, the date of PD will be the date of the initial abnormal FDG-PET scan).

If the positive FDG-PET at follow-up corresponds to a pre-existing site of disease on CT that is not progressing on the basis of the anatomic images, this is not PD.

Determination of Overall Response by the RECIST 1.1 Criteria

When both target and non-target lesions are present, individual assessments will be recorded separately. The overall assessment of response will involve all parameters as depicted in the following table.

Response Evaluation Criteria in Solid Tumors by RECIST 1.1

Target Lesions	Non-target Lesions	New Lesions	Overall Response
CR	CR	No	CR
CR	Non-CR/non-PD	No	PR
CR	Not evaluated	No	PR
PR	Non-PD or not all evaluated	No	PR
SD	Non-PD or not all evaluated	No	SD
Not all evaluated	Non-PD	No	NE
PD	Any	Yes or No	PD
Any	PD	Yes or No	PD
Any	Any	Yes	PD

CR = complete response, PR = partial response, SD = stable disease,

PD = progressive disease, and NE = inevaluable.

Best overall response

The best overall response is defined according to the tumor response along the study. Complete or partial responses may be claimed only if the criteria for each are met at a following time point as specified in the protocol (generally 4 weeks later). In this circumstance, the best overall response can be interpreted as the following table.

Best Overall Response When Confirmation of CR and PR Required

Overall response First time point	Overall response Subsequent time point	BEST overall response
CR	CR	CR
CR	PR	SD, PD or PR ^a
CR	SD	SD provided minimum criteria for SD duration met, otherwise, PD
CR	PD	SD provided minimum criteria for SD duration met, otherwise, PD
CR	NE	SD provided minimum criteria for SD duration met, otherwise NE
PR	CR	PR
PR	PR	PR
PR	SD	SD
PR	PD	SD provided minimum criteria for SD duration met, otherwise, PD
PR	NE	SD provided minimum criteria for SD duration met, otherwise NE
NE	NE	NE

CR = complete response, PR = partial response, SD = stable disease,

PD = progressive disease, and NE = inevaluable.

a If a CR is truly met at first time point, then any disease seen at a subsequent time point, even disease meeting PR criteria relative to baseline, makes the disease PD at that point (since disease must have reappeared after CR). Best response would depend on whether minimum duration for SD was met. However, sometimes 'CR' may be claimed when subsequent scans suggest small lesions were likely still present and in fact the patient had PR, not CR at the first time point. Under these circumstances, the original CR should be changed to PR and the best response is PR.

Patients with a global deterioration of health status requiring discontinuation of treatment without objective evidence of disease progression at that time should be reported as 'symptomatic deterioration'. Every effort should be made to document objective progression even after discontinuation of treatment. Symptomatic deterioration is not a descriptor of an objective response: it is a reason for stopping study therapy. The objective response status of such patients is to be determined by evaluation of target and non-target lesions.

In some circumstances it may be difficult to distinguish residual disease from normal tissue. When the evaluation of CR depends upon this determination, it is recommended that the residual lesion be investigated (fine needle aspirate/biopsy) before assigning a status of complete response. FDG-PET may be used to upgrade a response to a CR in a manner

similar to a biopsy in cases where a residual radiographic abnormality is thought to represent fibrosis or scarring. The use of FDG-PET in this circumstance should be prospectively described in the protocol and supported by disease specific medical literature for the indication. However, it must be acknowledged that both approaches may lead to false positive CR due to limitations of FDG-PET and biopsy resolution/sensitivity.

9.5. Prostate Cancer Working Group 2 (PCWG2) – Soft Tissue Response Criteria

Adapted from Scher H.I., et al: Design and End Points of Clinical Trials for Patients with Progressive Prostate Cancer and Castrate Levels of Testosterone: Recommendations of the Prostate Cancer Clinical Trials Working Group. *J Clin Oncol.* 26 (2008) 1148-1159.

[figure not shown]
And Eisenhauer E.A., et al: New response evaluation criteria in solid tumors: Revised RECIST guideline (version 1.1). *European Journal of Cancer* 45 (2009) 228–247.

Evidence of PD to Determine CRPC Eligibility

Patients being considered for trial entry should have evidence of disease progression by either PSA, RECIST, or bone scan to be eligible.

PSA: PSA evidence of disease progression based on the prostate cancer working group (PCWG) 2 criteria consist of a minimum PSA level 2.0 ng/ml that has risen on at least 2 successive occasions, at least 1 week apart. The reference value #1 is the last value before the rise in PSA was observed. If the confirmatory PSA value (Figure 2, #3A) is greater than the screening value then progression by PSA is met and the patient is eligible for trial enrollment on the basis of PSA alone. If the confirmatory PSA (Figure 2, #3B) value is less than the screening PSA (Figure 2, #2) value, then an additional test for rising PSA (#4) will be required to document progression before the patient can be enrolled.

Figure 2. Change in PSA

Target lesion/measurable disease: Patients are not required to have evidence of disease progression by measurable disease if they meet the criteria for disease progression on the basis of PSA or bone scan. Evidence of nodal or visceral disease RECIST 1.1 progression however is sufficient for trial entry independent of PSA readings. Because lymph nodes may be enlarged due to benign pathology, only lymph nodes that are ≥ 2.0 cm should be used for disease evaluation.

Bone scan: Evidence of disease progression based on bone scan appearance is sufficient for trial entry independent of PSA readings. If the appearance of the bone scan is the only indicator of progression, then there must be ≥ 2 new bone lesions compared with the prior bone scans. If there is ambiguity about the appearance of the bony lesions such as traumatic in nature or secondary to a flare reaction, then it is recommended that an alternative imaging modality such as MRI or fine-cut CT be used to evaluate these lesions further.

CRITERIA FOR OUTCOME MEASURES:

Soft-tissue lesions: Use RECIST with caveats,

- Only report changes in lymph nodes that were ≥ 2.0 cm in diameter at baseline;
- Record changes in nodal and visceral soft tissue sites separately;
- Record complete elimination of disease at any site separately;
- Confirm favorable change with second scan.

Bone:

- Record outcome as new lesion or no new lesions

Criteria for Evidence of Radiographic Progression

Bone disease will be assessed for progressive disease only by PCWG2. The documentation required for the determination of radiographic progression is shown in the table below.

Date Progression Detected ^[1]	Criteria for Progression	Criteria to Confirm Progression	Criteria to Document Disease Progression on Confirmatory Scan
Week 9	Bone lesions: 2 or more new lesions compared to screening bone scan by PCWG2	Timing: At least 6 weeks after progression identified or at Week 16 visit ^[2]	2 or more new bone lesions on bone scan compared to Week 8 scan
	Soft tissue lesions: Progressive disease on CT or MRI by RECIST v1.1	No confirmatory scan required for soft tissue disease progression	No confirmatory scan required for soft tissue disease progression
Week 18 or later	Bone lesions: 2 or more new lesions on bone scan compared to Week 8 bone scan	Timing: At least 6 weeks after progression identified or at next imaging time point ^[2]	Persistent or increase in number of bone lesions on bone scan compared to prior scan ^[3]

Date Progression Detected ^[1]	Criteria for Progression	Criteria to Confirm Progression	Criteria to Document Disease Progression on Confirmatory Scan
	Soft tissue lesions: Progressive disease on CT or MRI by RECIST v1.1	No confirmatory scan required for soft tissue disease progression	No confirmatory scan required for soft tissue disease progression

[1] Progression detected by bone scan at an unscheduled visit either before Week 8 or between scheduled visits will require a confirmatory scan at least 6 weeks later and should follow confirmation criteria outlined in the table for the next scheduled scan.

[2] Confirmation must occur at the next available scan.

[3] For confirmation, at least 2 of the lesions first identified as new must be present at the next available scan (confirmation scan).

Disease progression in bone must be confirmed at least 6 weeks later, as per PCWG2. See table below for the timing of confirmatory imaging requirements.

Confirmatory Imaging Requirements for Patients With CRPC Based on RECIST v1.1 and PCWG2

Disease Site	Response	Progression ^[1]
Soft tissue	Must be confirmed at least 4 weeks later	No confirmation required
Bone	Not applicable	Must be confirmed at least 6 weeks later

[1] To inform permanent treatment discontinuation.

Objective Response Status at Each Evaluation

Target Lesions	Non-target Disease	New Lesions	Objective status
CR	CR	No	CR
CR	Non-CR/Non-PD	No	PR
CR	Indeterminate or Missing	No	PR
PR	Non-CR/Non-PD, Indeterminate, or Missing	No	PR
SD	Non-CR/Non-PD, Indeterminate, or Missing	No	Stable
Indeterminate or Missing	Non-PD	No	Indeterminate
PD	Any	Yes or No, including bone determination	PD
Any	PD	Yes or No	PD
Any	Any	Yes	PD

If there is a protocol deviation and a patient has been enrolled allows enrollment of patients with only non-target disease, the following table will be used:

Objective Response Status at Each Evaluation for Patients With Non-Target Disease Only

Non-target Disease	New Lesions	Objective status
CR	No	CR
Non-CR/Non-PD	No	Non-CR/Non-PD
Indeterminate	No	Indeterminate
Unequivocal progression	Yes or No	PD
Any	Yes	PD

Procedures for Assessing PSA Response/Progression Post Study Treatment

PSA measurements will be performed on C1D1 (± 14 days) and Day 1 of Cycle 4, 7, 10 and every third cycle thereafter, as well as at the End of Treatment visit. Increases and decreases will be tracked in order to assess disease response. The PSA readings on its own will not be used to define progression in this protocol. PSA response and PSA progression will be defined according to the consensus guidelines of the PCWG2:

- PSA partial response is defined as a $\geq 50\%$ decline in PSA from Cycle 1 Day 1 (baseline) PSA value. This PSA decline must be confirmed to be sustained by a second PSA value obtained 4 or more weeks later.
- PSA progression date is defined as the date that a $\geq 25\%$ increase and an absolute increase of ≥ 2 ng/mL above the nadir is documented, which is confirmed by a second consecutive value obtained 4 or more weeks later. The first PSA reading will be obtained at week 12.

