 To confirm PF-06952229 safety profile in combination with enzalutamide at the estimated RP2D in patients with mCRPC. To estimate efficacy of PF-06952229 in combination with enzalutamide at the estimated RP2D in patients with mCRPC. To confirm the RP2D of PF-06952229 in combination with enzalutamide in patients with mCRPC. 	 AEs as graded by NCI CTCAE version 5.0. Laboratory abnormalities as graded by NCI CTCAE version 5.0. PSA50 Response Rate. Response assessment will be based on PCWG2 and RECIST 1.1.
Secondary Objective(s):	Secondary Endpoint(s):
 To estimate additional efficacy of PF-06952229 at the estimated RP2D in patients with mCRPC. To further evaluate the PK of PF-06952229 when given in combination with enzalutamide. To evaluate immune cells in paired pre and post treatment tumor biopsies (where available). 	 ORR based on PCWG2 and RECIST 1.1. and time to event endpoints (DoR, PFS, OS, TTP, TTR). Pharmacokinetic parameters of PF-06952229 (in at least 8 subjects). Single Dose (SD) - C_{max}, T_{max}, AUC_{last}, and as data permit, AUC_{inf}, CL/F, V_z/F, and t_{1/2}. Multiple Dose (MD) - C_{ss,max}, T_{ss,max}, AUC_{last}, C_{ss,min}, and as data permit CL_{ss}/F, V_{ss}/F, t_{1/2}, and R_{ac} (AUC_{last}/AUC_{last}). Peak and trough concentrations at selected cycles. Assessment of levels of intra-tumor T cells (eg, CD8 IHC);

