4.1. Inclusion Criteria

Patients must meet all of the following inclusion criteria to be eligible for enrollment in the study:

- 1. For Part 1A (monotherapy dose escalation phase): Histological or cytological diagnosis of a solid tumor that is advanced/metastatic, patients are intolerant to standard treatment, resistant to standard therapy or for which no standard therapy is available for the following tumor types:
 - Breast cancer;
 - Prostate cancer (mCRPC testosterone less than 50 ng/dL);
 - Squamous cell cancer of the head and neck;
 - Melanoma;
 - Mesothelioma;
 - Pancreatic cancer;
 - Colorectal cancer;
 - Renal cell carcinoma;
 - Hepatocellular cancer.

2. For Part 1B (Combination Dose Escalation Phase): histological or cytological diagnosis of mCRPC (castration is defined as having a serum testosterone less than 50 ng/dL due to medical or surgical castration), patients who are intolerant to standard treatment, resistant to standard therapy, or refuse to standard therapy.

3. Part 2A and Part 2B:

- Histologically or cytologically confirmed prostate adenocarcinoma metastatic disease.
- Effective castration with serum testosterone levels <0.5 ng/mL (1.7 nmol/L).
- Having received 3 or more cycles of prior docetaxel therapy (before or after abiraterone).
- Having PD while receiving abiraterone acetate within 12 months of abiraterone treatment initiation (≤12 months).
- Progressive disease (PD) by:
 - a. Progression in measurable disease per RECIST 1.1 criteria. Patient with measurable disease must have at least 1 lesion that can be accurately measured in at least 1 dimension (longest diameter to be recorded). Each lesion must be at least 10 mm when measured by computed tomography (CT) (CT scan thickness no greater than 5 mm) or magnetic resonance imaging (MRI). Lymph nodes should be ≥15 mm in short axis. As defined by PCWG2, if lymph node metastasis is the only evidence of metastasis, it must be ≥20 mm in diameter when measured by spiral CT or MRI. Previously irradiated lesions, primary prostate lesion, and bone lesions will be considered non-measurable disease, or
 - b. Appearance of 2 or more new bone lesions (PCWG2). They must be confirmed by other imaging modalities (CT; MRI) if ambiguous results, or

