Appendix 6. Response Evaluation Criteria In Solid Tumors (RECIST) v 1.1

Adapted from Eisenhauer E.A., et al: New response evaluation criteria in solid tumors: Revised RECIST guideline (version 1.1). European Journal of Cancer 45 (2009) 228–247.

CATEGORIZING LESIONS AT BASELINE

Measurable Lesions: Lesions that can be accurately measured in at least one dimension.

- Lesions with longest diameter twice the slice thickness and at least 10 mm or greater when assessed by CT or MRI (slice thickness 5-8 mm);
- Lesions with longest diameter at least 20 mm when assessed by Chest X-ray;
- Superficial lesions with longest diameter 10 mm or greater when assessed by caliper;
- Malignant lymph nodes with the short axis 15 mm or greater when assessed by CT.

NOTE: The shortest axis is used as the diameter for malignant lymph nodes, longest axis for all other measurable lesions.

Non-measurable disease

Non-measurable disease includes lesions too small to be considered measurable (including nodes with short axis between 10 and 14.9 mm) and truly non-measurable disease such as pleural or pericardial effusions, ascites, inflammatory breast disease, leptomeningeal disease, lymphangitic involvement of skin or lung, clinical lesions that cannot be accurately measured with calipers, abdominal masses identified by physical exam that are not measurable by reproducible imaging techniques.

- Bone disease: Bone disease is non-measurable with the exception of soft tissue components that can be evaluated by CT or MRI and meet the definition of measurability at baseline;
- Previous local treatment: A previously irradiated lesion (or lesion subjected to other local treatment) is non-measurable unless it has progressed since completion of treatment.

Normal sites

- Cystic lesions: Simple cysts should not be considered as malignant lesions and should not be recorded either as target or non-target disease. Cystic lesions thought to represent cystic metastases can be measurable lesions, if they meet the specific definition above. If non-cystic lesions are also present, these are preferred as target lesions;
- Normal nodes: Nodes with short axis <10 mm are considered normal and should not be recorded or followed either as measurable or non-measurable disease.

RECORDING TUMOR ASSESSMENTS

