6.3. Analysis for Secondary Endpoints

6.3.1. Efficacy Endpoints Analysis

ORR, as assessed using PCWG2 for prostate cancer and RECIST version 1.1 for other tumor types, is a key efficacy endpoint. The following analyses will be performed in the mITT population by tumor type and pooled:

The ORR, along with other efficacy analyses will be performed in the mITT population. Part 1 and Part 2 data will be summarized separately, and may also be pooled together for analysis if deemed necessary. Specifically, the key tables in Part 2 include:

1. ORR by visit: investigator provided tumor response CR, PR, and CR+PR will be presented by descriptive statistics (frequency and percentage) and 95% confidence interval.
2. Best overall response of CR, PR, and CR+PR. This will include best overall response derivation without confirmation and with confirmation. Descriptive statistics (frequency and percentage) and 95% confidence interval will be provided.

Tumor response data in Part 1, Part 2 and across the two Parts may be summarized with descriptive statistics (frequency and percentage) in the following groups by visit and then best overall response across all visits:

- Overall summary for all doses and all tumor types;
- By tumor type regardless of dose;
- By dose regardless of tumor type;
- By dose and tumor type if data permit.

Summary tables of best overall response rate, PFS, OS, DOSD, and DOR may be provided by the groups aforementioned when deemed necessary (eg, if there are ≥ 5 patients in a specific group).

In addition, PSA50 Response Rate defined as $\geq 50\%$ PSA reduction from baseline assessed by PCWG2 for prostate cancer patients will be summarized similarly as ORR. See [Section 9.5](#) for more details on PSA measurement.

Efficacy listings (tumor measurements listings and tumor response listings) will be provided that include the investigator provided tumor measurement data, tumor response, best overall response, first CR/PR date, last date with CR or PR, most recent date without progression, progression date, death date, and last tumor assessment date, etc.

Endpoint	Analysis Set	Statistical Method	Model/Covariates/Strata	Missing Data
Overall response	mITT	Exact CI	See aforementioned summary descriptions on data pooling across dose and tumor type	Observed case
Overall Survival	ITT	Kaplan-Meier	See aforementioned summary descriptions on data pooling across dose and tumor type	Censored at last visit

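### In mCRPC, ORR is scored only on lymph nodes of 2.0 cm or more but analysed in all mITT patients, so patients with bone disease whose only measurable lesions are 15–19 mm nodes count as non-responders with practically no route to response

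*SAP*

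**What the plan says.** **Criterion for response.** SAP 6.3.1: "ORR, as assessed using PCWG2 for prostate cancer and RECIST version 1.1 for other tumor types, is a key efficacy endpoint". SAP 3.2, 5.3.2 and 6 make the same split by tumour type. Protocol section 2 words the Part 2 secondary endpoint differently: "ORR based on PCWG2 and RECIST 1.1. and time to event endpoints".

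**Nodes under PCWG2.** Protocol Appendix 7 and SAP 9.5 apply RECIST to soft tissue with caveats. One caveat is: "Only report changes in lymph nodes that were ≥ 2.0 cm in diameter at baseline". The same appendices limit disease evaluation to nodes of that size. Bone is assessed for progression only, and its response entry is given as not applicable.

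**Nodes elsewhere.** Protocol Inclusion 3a: "Lymph nodes should be ≥15 mm in short axis". The next sentence adds that "if lymph node metastasis is the only evidence of metastasis, it must be ≥20 mm in diameter when measured by spiral CT or MRI". Protocol Appendix 6 lists as measurable: "Malignant lymph nodes with the short axis 15 mm or greater when assessed by CT". SAP 9.4 gives "15 mm in short axis for lymph nodes when assessed by CT scan", and says such nodes "may be identified as target lesions if the criterion of a short axis of ≥ 15 mm by CT scan is met".

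**Denominator.** SAP 6.3.1 analyses ORR in mITT. SAP 4.4 defines mITT by at least one dose, a baseline assessment, and a post-baseline assessment, progression or early death. Measurable disease is not mentioned.

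**Sizing.** Protocol 9.6.2 and SAP 5.2.3 assume that 80% of 20 patients, that is 16, have measurable disease and are response evaluable, with 7 of 16 responding.

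**The concern.** The rule that decides who can respond and the rule that decides who is counted do not match. Numerator eligibility follows PCWG2 (nodes of 2.0 cm or more). The planning denominator uses the word measurable, which the rest of the documents tie to 15 mm. The analysis denominator has no such condition at all.

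The group caught is narrow but plausible in mCRPC: bone metastases plus nodes of 15–19 mm and no other measurable lesion. The 20 mm sentence in Inclusion 3a does not keep them out, because nodes are not their only metastasis, and they can also enter on bone or PSA progression (3b, 3c). With about 16 evaluable patients, a few people of this kind move the reported ORR noticeably, and always downward relative to the plan's own basis. No text says whether their nodes are recorded as target, as non-target, or not at all.

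**Working it through.** **1. Routes to response for a patient with bone disease and one 17 mm node.**
- Nodal shrinkage: not reported under SAP 9.5, because the node is below 2.0 cm.
- Bone: progression only.
- Non-target-only table in SAP 9.5: introduced as a protocol-deviation case. It has no PR row. CR needs all non-target lesions to disappear and, by the non-target definition in SAP 9.4, the tumour marker to normalise.
- Result: no route to PR, and only a remote one to CR. The patient remains in mITT.

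A patient who also has a visceral target lesion, or a node of 2.0 cm or more, can respond on that lesion.

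**2. The plan's own figure.** Inputs from Protocol 9.6.2: 0.8 × 20 = 16; 7/16 = 43.75%; threshold 30%; Uniform(0,1) prior, i.e. Beta(1,1). For x responders among n,

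P(ORR > 0.30) = 1 − BetaCDF(0.30; 1 + x, 1 + n − x).

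With 7/16 this is 1 − BetaCDF(0.30; 8, 10) = 0.895. The plan states 86.89%, which does not reproduce under the stated prior. It does reproduce with Beta(0,0), i.e. 1 − BetaCDF(0.30; 7, 9) = 0.869. That is a separate matter. I use the stated uniform prior throughout.

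**3. Effect of the node rule.** Let k of the 16 have only 15–19 mm nodes as measurable disease. The documents do not give k, so I show 0 to 6. Assume 43.75% of the other 16 − k respond, rounded to whole patients. For example, k = 2 gives 0.4375 × 14 = 6.1, so 6; k = 4 gives 0.4375 × 12 = 5.25, so 5.

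| k | Kept as non-responders | P(ORR > 30%) | PCWG2-evaluable only | P(ORR > 30%) |
|---|---|---|---|---|
| 0 | 7/16 (43.75%) | 0.895 | 7/16 | 0.895 |
| 2 | 6/16 (37.5%) | 0.775 | 6/14 (42.9%) | 0.869 |
| 4 | 5/16 (31.3%) | 0.597 | 5/12 (41.7%) | 0.835 |
| 6 | 4/16 (25.0%) | 0.389 | 4/10 (40.0%) | 0.790 |

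The left pair shows what the plan as written does to these patients. The right pair shows the proposed denominator: the rate stays near its planned value and the probability falls mainly because n is smaller. The 0.869 at k = 2 equals the plan's figure only because 6/14 under a uniform prior is also a Beta(7, 9) posterior.

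**4. Why 16 and not 20.** Holding the denominator at 16 isolates the node effect. If all 20 patients enter mITT, the four assumed to lack measurable disease are counted too: 7/20 = 35%, probability 0.723, before any node problem. The same missing condition causes both.

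**The case against.** The case on the other side is substantial and narrows the point.

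- PCWG2 is written as a disease-specific modification of RECIST, and the SAP assigns it to prostate cancer. A general 15 mm rule with a 2.0 cm override is not a contradiction. This stands: which threshold governs mCRPC scoring is clear.
- Inclusion 3a concerns progression at entry, not evaluability for ORR, and already requires 20 mm in node-only disease. This stands, so no change to eligibility is needed.
- The 2.0 cm rule gives no axis, so a node of 15–19 mm in short axis might seem to qualify on its long diameter. The note in Appendix 6 answers this: the shortest axis serves as the diameter for malignant nodes. SAP 9.5 does not repeat it, and should.
- The denominator is fixed as mITT. A reader might infer that the plan as written lets the analyst drop these patients and report, say, 5/14 or 7/14. It does not.
- A reader might infer that the SAP has dropped a RECIST ORR that the protocol requires. The protocol's naming of both criteria can equally mean one composite criterion, since Appendix 7 is built on both. No text demands two separate rates.
- ORR is secondary, SAP 5.1 states no hypotheses, and no decision rule is attached to the posterior probability. This limits the importance of the point but does not remove the bias in the estimate.

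None of this gives the bone-plus-small-node patient a practical way to respond, or takes that patient out of the denominator.

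**Conclusion.** The point holds for one subgroup: mCRPC patients with bone disease whose only measurable lesions are nodes of 15–19 mm in short axis. Followed exactly, the plan counts them as non-responders and pulls ORR below the basis on which Part 2B was sized.

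The size depends on k, which the documents do not give. In the planning case P(ORR > 30%) goes from 0.895 to 0.775 with two such patients and to 0.597 with four. This assumes that measurable in the sizing text carries its Inclusion 3a meaning, that 43.75% of the remaining patients respond, and that the uniform prior applies.

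A reader might infer that anyone with a 15–19 mm node can never respond. The documents do not support that: visceral lesions and larger nodes still count. PSA50, the primary efficacy measure in Part 2, does not depend on nodes. This is a cheap improvement to a secondary estimate, not a flaw in the trial's main conclusions.

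**What to change.** In SAP 6.3.1 and 9.5:

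1. Report the mCRPC ORR in patients with at least one baseline target lesion under the PCWG2 rule, with nodes of 20 mm or more. State that the short axis is meant, as in the Appendix 6 note.
2. Keep the mITT ORR as a supportive result.
3. State how nodes of 15–19 mm are recorded in mCRPC patients: target, non-target or not recorded.
4. As a sensitivity table, give ORR by unmodified RECIST 1.1 (15 mm short axis) with its own matching denominator, where those nodes were measured. The protocol names both criteria for Part 2, so this covers either reading.

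The cost is some wording, one extra table and a slightly smaller main denominator, hence a somewhat wider interval. Inclusion 3a can stay as it is. The rule should be fixed before the responses are analysed, because the study is open label and a later choice would be made with the outcomes known.
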